8.3.2 Investigator reporting: Notifying the FDA

n/a

8.4 Unmasking/Unblinding Procedures

n/a

8.5 Stopping Rules

The study will stop for an individual patient if any of the following occur:

1. The participant decides to withdraw from the study.
2. The participant experiences a Serious Adverse Event (SAE) that, in the opinion of the investigator, is possibly, probably or definitely related to the study drug utilizing the National Cancer Institute's CTCAE system as a guide.
3. The participant experiences a UPIRTSO AND, in the opinion of the investigator and study adjudicator, is related to the study drug
4. The participant experiences a grade 3 or higher CTCAE develop that are determined to be possibly or likely attributable to study drug
5. The participant experiences a medical condition that, in the opinion of the investigator, continuation on the study drug would be detrimental.
6. Decision by the DSMB. If a participant experiences a MELD-Na score increase by more than 5 points from baseline or doubling bilirubin level from enrollment, the DSMB will review the records to determine whether DILI is suspected or changes are attributed to natural course of disease
7. The participant experiences an increase of AST or ALT >500 U/L

Determination of whether worsening of liver biochemical tests is due to the alcoholic hepatitis or study drug induced liver injury (DILI) is difficult. An AST or ALT increase >500 IU/L would be considered an indication that the patient might have DILI since AST and ALT are typically < 300-400 U/L in AH. Such an increase of > 500 IU/L would trigger prompt evaluation and consideration of discontinuation of the study drug. Considering how difficult it is to distinguish potential DILI from worsening of the underlying liver disease, we have incorporated an external adjudication of all suspected DILI events. An increase in MELD-Na score >5 points from baseline, or doubling bilirubin (2 times the baseline level at enrollment) would warrant urgent review by the DSMB.

The study will be put on hold for review with the DSMB if one patient experiences a serious adverse event. The study will be restarted if the DSMB considers the serious adverse events to be unrelated to study drug.

The study will stop overall if any of the following occur:

1. The participant experiences a Serious Adverse Event (SAE) that, in the opinion of the investigator, is possibly, probably or definitely related to the study drug utilizing the National Cancer Institute's CTCAE system as a guide.
2. Two or more patients have an adverse event grade 3 or above on the CTCAE scale that is determined to be possibly or likely attributable to study drug as per the study adjudicator.
3. Three or more patients develop AST or ALT > 500 U/L.
4. If recommended by the DSMB.

In the event of a SAE, the site will report this to the Mayo Clinic study team. If the SAE is attributable to study drug, the Mayo Clinic study team will report the event to the Institutional Review Board.

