Acamprosate has not been evaluated formally in individuals with AUD and liver disease. It is an N-methyl-D-aspartate glutamate receptor antagonist approved by the Food and Drug Administration to aid in maintaining abstinence in individuals with alcohol dependence (Frye et al., 2016). Acamprosate has an unclear mechanism of action, although it is thought that its effect on decreased alcohol craving intensity is mediated through a reduction in glutamate levels (Frye et al., 2016). The efficacy of acamprosate has been demonstrated in several meta-analyses, most recently exhibiting a number needed to treat of 12 to prevent return to any drinking (Jonas et al., 2014; Rosato et al., 2015). Acamprosate is not metabolized by the liver and thus has been considered as a potential therapeutic option in those with liver disease. However, as acamprosate antagonizes the glutamate receptor, there have been concerns it may increase the risk of hepatic encephalopathy. Previously, a single dose of acamprosate 666 mg was administered to 12 patients with Child-Pugh A or B cirrhosis with no identifiable induction of subclinical hepatic encephalopathy; however, transient diastolic hypotension was noted (Delgrange et al., 1992). No further studies on acamprosate have been performed in individuals with liver disease.

To evaluate the safety of acamprosate in individuals with AUD and alcohol-related liver disease, an initial pilot study in five patients with a Model for End Stage Liver Disease Sodium (MELD-Na) score less than 20 will be conducted. If no safety concerns are identified, the study will then

be performed in five patients with MELD-Na scores of 20 or more. If again no safety concerns are identified, a larger, placebo-controlled efficacy study is planned and will be submitted as a separate protocol.

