Study duration will be six months. During the study, patients will complete monthly MELD-Na labs and receive a phone call weekly for the first month, then monthly for a total of 3 months. Urine ethyl glucuronide will be done at enrollment and once monthly. Patients will then have a follow up visit at 12 weeks, with labs, urine ethyl glucuronide, vital signs and physical exam. During telephone assessments and at the follow up visit, patients will be asked about potential side effects and hepatic decompensation. Other variables to be collected at enrollment and at the 3 month visit include Child-Pugh score, West Haven grading of HE, vital signs at enrollment and current medications. At enrollment, during phone calls and at the follow up visit, patients will be asked standardized questions to assess for HE based on the abbreviated telephone version of the mini-mental state examination (MMSE). Follow up telephone visits at 13 and 24 weeks will be conducted, primarily to monitor for adverse events and alcohol relapse.

The Pennsylvania Alcohol Craving Scale (PACS) will be applied before treatment initiation, weekly for the first month on treatment, then monthly thereafter. This will include the need severity scale (mild, moderate, severe) at baseline and at each assessment by phone call and in clinic.

Alcohol use relapse will be monitored. Any amount of alcohol use as revealed during follow-up considered a relapse event. Alcohol use will be captured and categorized as none, slip (no longer drinking at most recent follow up) or sustained alcohol use (minimum 100 days drinking). Slips and sustained alcohol use will be categorized as binge drinking, frequent drinking, or both (binge drinking as more than 6 units/day for men and 4 units/day for women and frequent drinking as alcohol use in 4 or more days/week regardless of quantity per day) (Lee et al., 2018).

Basic descriptive statistics and a qualitative analysis will be performed. Analyses will be performed using SPSS 25 (Chicago, IL). Results will not contain any patient-specific information.

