5.2 Treatment Regimen

Acamprosate will be dosed at 333 mg PO TID, increased to 666 mg PO TID after 1 week if tolerated. If GFR is 30-50 ml/min, dosage will remain at 333 mg PO TID throughout the study. Treatment duration is 3 months.

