6.2 Visit 2-5

Visits 2-5 will be conducted by telephone and include data to be included on the Case Report Form including

- Clinical history
- Adverse events
- Medication list including new medications, change in medications
- Alcohol use
- Other substance use including nicotine and recreational drug use
- PACS responses and score
- MMSE responses and score
- West Haven HE grade
- Laboratory results and clinical interpretation of the values.
- Clinical significance of observations (when applicable)

6.3 Visit 6

Visit 6 will occur at week 12 of acamprosate therapy. Interval clinical history, adverse events, medication list and alcohol and other substance use will be detailed. PACS score will be evaluated. Case Report Form will be completed.

Vital signs and a physical examination will be performed. West Haven HE score will be graded and modified telephone version of MMSE completed. Blood work will be completed including a complete blood count, electrolytes, creatinine, blood urea nitrogen, total bilirubin, direct bilirubin, albumin, INR, AST, ALT and alkaline phosphatase.

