6.5 Visit 8 Follow up

Patients will receive a telephone call at week 24 for reassessment. Interval clinical history will be obtained, history of any serious adverse events, medication list and alcohol and other substance use will be detailed. PACS score, modified telephone version of MMSE and West Haven HE score will be calculated. Case Report Form will be completed. Final blood tests will be requested.

	Screening/ Enrollment day	Treatment Period													
		W1	W2	W3	W4	W5	W6	W7	W8	W9	W10	W11	W12	W13	W24
Test/Procedure Name	(D1)														
Study Visit	x													x	
Follow-Up Phone Calls		x	x	x	x				x					x	x
Physical Exam	x													x	
Complete blood count	x													x	x
Electrolytes	x				x				x				x		x
Creatinine	x				x				x				x		x
Urea	x												x		x
Total Bilirubin	x				x				x				x		x
Direct bilirubin	x												x		x
INR	x				x				x				x		x
Urine Ethyl Glucuronide	x				x				x				x		x
Albumin	x												x		x
AST, ALT, alkaline phosphatase	x												x		x
Child Pugh Score	x												x		x
West Haven HE Score	x												x	x	x
MMSE	x	x	x	x	x				x				x	x	x
Med Review	x	x	x	x	x				x				x	x	x
Pennsylvania Alcohol Craving Scale	x	x	x	x	x				x				x	x	x

Adverse event evaluation	x	x	x	x	x			x			x	x	x
Alcohol consumption documentation	x	x	x	x	x			x			x	x	x

7 Statistical Plan

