A preexisting condition is one that is present at the start of the study. A preexisting condition will be recorded as an adverse event if the frequency, intensity, or the character of the condition worsens during the study period.

General Physical Examination Findings

At screening, any clinically significant abnormality will be recorded as a preexisting condition. At the end of the study, any new clinically significant findings/abnormalities that meet the definition of an adverse event must also be recorded and documented as an adverse event.

Post-study Adverse Event

All unresolved adverse events will be followed by the investigator until the events are resolved, the subject is lost to follow-up, or the adverse event is otherwise explained. At the last scheduled visit, the investigator should instruct each subject to report, to the investigator, any subsequent event(s) that the subject, or the subject's personal physician, believes might reasonably be related to participation in this study.

Abnormal Laboratory Values

Determination of whether worsening of liver biochemical tests is due to the alcohol-related hepatitis or study drug induced liver injury (DILI) is difficult. An AST or ALT increase >500 IU/L would be considered an indication that the patient might have DILI since AST and ALT are typically $< 300-400$ U/L in AH. Such an increase of > 500 IU/L would trigger prompt evaluation and consideration of discontinuation of the study drug. Considering how difficult it is to distinguish potential DILI from worsening of the underlying liver disease, we have incorporated an external adjudication of all suspected DILI events. An increase in MELD-Na score >5 points from baseline, or doubling bilirubin (2 times the baseline level at enrollment) would warrant urgent review by the DSMB.

The study will be **stopped** if three or more patients develop AST or ALT > 500 U/L or as or as determined by the DSMB.

Hospitalization, Prolonged Hospitalization or Surgery

Any adverse event that results in hospitalization or prolonged hospitalization will be documented and reported as a serious adverse event unless specifically instructed otherwise in this protocol. Any condition responsible for surgery will be documented as an adverse event if the condition meets the criteria for an adverse event.

Neither the condition, hospitalization, prolonged hospitalization, nor surgery are reported as an adverse event in the following circumstances:

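### AST/ALT is not scheduled between enrollment and week 12, so the individual stop at AST/ALT >500 U/L has no scheduled data until dosing is nearly over

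*Combined protocol and SAP*

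**What the plan says.** Two stopping rules depend on transaminases. Item 7 of the individual rules in Section 8.5 reads "The participant experiences an increase of AST or ALT >500 U/L". Item 3 of the overall rules reads "Three or more patients develop AST or ALT > 500 U/L", and Section 8.1 (Abnormal Laboratory Values) repeats it: the study stops "if three or more patients develop AST or ALT > 500 U/L". Both sections treat a rise of this size as a possible sign of drug-induced liver injury that calls for prompt evaluation.

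The measurements are set out elsewhere:

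- **Section 3.1** says that during the study "patients will complete monthly MELD-Na labs".
- **Section 6.1** names AST and ALT at enrollment.
- **Section 6.2** makes Visits 2-5 telephone contacts. Laboratory results go on the CRF, but no AST/ALT draw is named.
- **Section 6.3** names AST and ALT again: "Visit 6 will occur at week 12 of acamprosate therapy".
- **The schedule table after Section 6.5** has a row "AST, ALT, alkaline phosphatase" with three marks. Electrolytes, creatinine, total bilirubin and INR have five each.

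On dosing, Section 5.2 states "Treatment duration is 3 months". On escalation, Section 1.1 makes the MELD-Na 20-or-more cohort conditional on the first five patients: "If no safety concerns are identified, the study will then" proceed to five patients with the higher scores.

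**The concern.** A rule meant to stop dosing needs data while there is still dosing to stop. Here the laboratory value that triggers item 7 is not scheduled until the end-of-treatment visit. A patient whose AST or ALT passes 500 U/L in weeks 1 to 11 could continue on the drug unnoticed unless something else prompts a blood test.

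Safety is the primary endpoint, and Section 3.4 lists blood work among its parameters. A transient rise that settles before week 12 could therefore be missing from the trial's main result. It could also be missing from the evidence used to decide whether patients with more severe liver disease may enter.

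**Working it through.** The plan states no figure on this point, so there is none to reproduce. The check compares the schedule with the rules and then measures the gap.

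**1. When AST/ALT is scheduled.** By column position, the three AST/ALT marks fall at day 1, W12 and W24. The five marks for total bilirubin and INR fall at day 1, W4, W8, W12 and W24. Some rows of the extracted table look shifted: the study visit and physical examination appear under W13, while the text puts that visit at week 12. Column position alone should therefore not carry the argument. The mark counts (three against five) and the text of Sections 3.1, 6.1 and 6.3 lead to the same reading: enrollment, week 12 and the off-drug follow-up.

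**2. Share of dosing elapsed at the first on-treatment value.** Three months is taken as 84 to 91 days (an assumption).

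- Now, day 84: 84/84 = 100%; 84/91 = 92%.
- With W4 added, day 28: 28/84 = 33%; 28/91 = 31%.

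**3. Longest scheduled gap on treatment.** It is 12 weeks now and 4 weeks with W4 and W8 added.

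**4. Overall rule 3.** On scheduled data, the earliest it can fire is the third patient's week 12 now, against the third patient's week 4 with the added tests. Week-12 values from early patients can still protect later ones.

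**5. Values available at the escalation decision.** If all five first-cohort patients have reached week 12, there are 5 × 1 = 5 on-treatment values now and 5 × 3 = 15 with W4 and W8. Section 1.1 does not fix the timing of the decision, so this count is conditional.

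**6. Illustration of what a draw would catch.** Assume that onset is uniform over the 12 weeks, that every draw is taken on schedule, that there are no unscheduled tests, and that a rise lasts D weeks (D < 12). The documents give no value for D, so a range is shown.

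- W12 only: probability = D/12.
- W4, W8 and W12: probability = min(D, 4)/4.

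| D (weeks) | Now | With W4 and W8 |
|---|---|---|
| 2 | 2/12 = 17% | 2/4 = 50% |
| 4 | 4/12 = 33% | 4/4 = 100% |
| 6 | 6/12 = 50% | 100% |
| 8 | 8/12 = 67% | 100% |

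For a sustained rise, the mean wait to the first scheduled value is 12/2 = 6 weeks now and 4/2 = 2 weeks with the added draws.

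**The case against.** The strongest reply is that sparse transaminase testing suits this drug. Sections 1.1 and 5.1 say that acamprosate is not metabolized by the liver, and the risks listed in Sections 1.6 and 3.1 include no hepatic injury. The concerns named for this population are encephalopathy and hypotension, and mental status is tested often. Bilirubin, INR, creatinine and electrolytes are drawn at weeks 4 and 8. A bilirubin doubling or a MELD-Na increase above 5 points brings urgent DSMB review, with liver injury explicitly in view. Symptoms are asked about at each contact, any SAE pauses the study, and related SAEs or grade 3 events stop dosing by other routes. What remains uncovered is a rise above 500 U/L with no symptoms and no bilirubin or MELD-Na signal.

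Most of this is fair. It limits how much harm can be inferred, and the documents give no basis for saying that missed liver injury is likely. It does not remove the mismatch: the sponsor listed AST/ALT >500 U/L as a separate stop, and Section 1.1 says that the drug has not been formally evaluated in these patients.

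Two further replies carry less weight. Section 3 speaks generally of monthly blood work, and the CRF list in Section 6.2 includes laboratory results, but neither orders AST/ALT. The DSMB charter was not available and might add monitoring, so the conclusion is confined to the protocol text.

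The caution about the detection table is sound. It rests on assumed onset, duration and perfect attendance. A 4-week rise spans exactly one draw interval, so a single late draw would undo its 100%. The table shows direction only.

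**Conclusion.** The concern holds. As written, individual rule 7 has no scheduled input until 92% to 100% of dosing has elapsed, and overall rule 3 is delayed until the third patient reaches week 12. The elapsed share and the 12-week gap follow from the schedule and the treatment duration; the only assumption is whether three months means 84 or 91 days. The detection probabilities are illustrative, and the escalation count is conditional on timing.

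The limits are clear. A sustained rise would still be found at week 12, an unscheduled test could trigger rule 7 earlier, and the monthly bilirubin and MELD-Na review gives partial cover. This should be fixed because a pre-stated safety stop lacks the data to operate and the remedy is cheap.

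A separate, lesser point concerns wording. Sections 8.1 and 8.5 express the threshold both as an increase of more than 500 and as a value above 500. Section 8.5 gives both a mandatory stop (item 7) and mere consideration of stopping (the paragraph below it). This adds nothing to the scheduling argument.

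**What to change.** Add AST and ALT to the existing W4 and W8 MELD-Na draws in the schedule table, and name them in Sections 3.1 and 6.2. If monthly AST/ALT was always intended, the table and text still need this correction.

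In the same amendment, use one threshold definition and one consequence throughout Sections 8.1 and 8.5. Which of them stands is the sponsor's clinical decision.

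The cost is a schedule and text amendment plus 2 assays × 10 completers = 20 AST/ALT assays. Section 4.4.1 replaces withdrawn patients, so the number could be somewhat higher: for example, up to 2 × 12 = 24 if 12 patients are treated. No visit or venipuncture is added.

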8.6 Medical Monitoring

It is the responsibility of the Principal Investigator to oversee the safety of the study at his/her site. This safety monitoring will include careful assessment and appropriate reporting of adverse events as noted above, as well as the construction and implementation of a site data and safety-monitoring plan (see section 10 “Study Monitoring, Auditing, and Inspecting”). Medical monitoring will include a regular assessment of the number and type of serious adverse events.

8.6.1 Internal Data and Safety Monitoring Board

See DSMB charter.

9 Data Handling and Record Keeping

9.1 Confidentiality

Information about study subjects will be kept confidential and managed according to the requirements of the Health Insurance Portability and Accountability Act of 1996 (HIPAA).

Those regulations require a signed subject authorization informing the subject of the following:

- What protected health information (PHI) will be collected from subjects in this study
- Who will have access to that information and why
- Who will use or disclose that information
- The rights of a research subject to revoke their authorization for use of their PHI.

In the event that a subject revokes authorization to collect or use PHI, the investigator, by regulation, retains the ability to use all information collected prior to the revocation of subject authorization. For subjects that have revoked authorization to collect or use PHI, attempts should be made to obtain permission to collect at least vital status (long term survival status that the subject is alive) at the end of their scheduled study period.

9.2 Source Documents

Source data is all information, original records of clinical findings, observations, or other activities in a clinical trial necessary for the reconstruction and evaluation of the trial. Source data are contained in source documents. Examples of these original documents, and data records include: hospital records, clinical and office charts, laboratory notes, memoranda, subjects' diaries or evaluation checklists, pharmacy dispensing records, recorded data from automated

instruments, copies or transcriptions certified after verification as being accurate and complete, microfiches, photographic negatives, microfilm or magnetic media, x-rays, subject files, and records kept at the pharmacy, at the laboratories, and at medico-technical departments involved in the clinical trial.

9.3 Case Report Forms

The study case report form (CRF) is the primary data collection instrument for the study. All data requested on the CRF must be recorded. All missing data must be explained. If a space on the CRF is left blank because the procedure was not done or the question was not asked, write “N/D”. If the item is not applicable to the individual case, write “N/A”. All entries should be printed legibly in black ink. If any entry error has been made, to correct such an error, draw a single straight line through the incorrect entry and enter the correct data above it. All such changes must be initialed and dated. Do not erase or use “white-out” for errors. For clarification of illegible or uncertain entries, print the clarification above the item, then initial and date it. If the reason for the correction is not clear or needs additional explanation, neatly include the details to justify the correction.

Data Management

Source documents will be kept that include, but are not limited to, medical records, charts, appointment books, patient questionnaires, original laboratory records, equipment printouts. All source documents must be made available to the CRA. The following data must be included in the source data:

- Consent to participate in Trial
- Letter to Primary Care Physician, if applicable
- Patient visit dates
- Screening Numbers
- Demographic Information
- Medical history
- Disease history
- Physical examination
- Vital signs
- Laboratory assessments (copy of laboratory reports)
- AEs and concomitant medications
- Dates of administering study medication
- Patient questionnaires responses
- Issues with protocol compliance
- Completion of, or withdrawal from, trial
- Entirety of Case Report Forms

Data Processing

This is a single center study. Flow of data will be between study coordinators and PIs. De-identified data will be available to DSMB.

Data Security and Confidentiality

All information obtained during the conduct of the trial with respect to the patient will be regarded as confidential and confidentiality of all patients will be maintained. Clinical monitors (e.g. CRAs), auditors and inspectors will require access to a patient's medical notes for the purpose of source document verification source document verification but the patient's confidentiality will be maintained at all times. An agreement for disclosure of any such information will be obtained in writing and is included in the statement of informed consent. The trial data shall not be disclosed to a third party (with the exception of auditors and/or regulatory authorities) without the written consent of the PIs. All data shall be secured against unauthorized access.

Apart from the investigators, no one will have access to participant's identity. The site will securely maintain the code that links participants' identity to their study numbers to prevent access to unauthorized third parties. Participants will be identified according to their study numbers in the data management system and by the investigators during any communications.

Data Quality Assurance

Logic and consistency checks will be performed on all data entered into the CRF to ensure accuracy and completeness.

Training sessions, regular monitoring of the trial, instruction manuals, data verification, cross-checking and data audits will be performed to ensure quality of all trial data.

Data Clarification Process

The data manager for the study will conduct periodic data queries.

